4.2.1 Acceptable non-hormonal birth control methods

- Total/true abstinence: When the patient refrains from any form of sexual intercourse and this is in line with their usual and/or preferred lifestyle; this must continue for the total duration of the study treatment and for at least 6 months (for individuals able to bear children) or at least 3 months (for individuals able to father children) after the last dose of study treatment. Periodic abstinence (eg, calendar ovulation, symptothermal, post-ovulation methods, or declaration of abstinence solely for the duration of a trial) and withdrawal are not acceptable methods of contraception.
- Vasectomised sexual partner PLUS condom (with participant assurance that partner received post-vasectomy confirmation of azoospermia).
- Tubal occlusion PLUS condom.
- Intrauterine device (provided coils are copper-banded) PLUS condom.

4.2.2 Acceptable hormonal methods

- Mini pill PLUS condom: Progesterone-based oral contraceptive pill using desogestrel. Cerazette (Merck Sharp & Dohme) is currently the only highly efficacious progesterone-based pill available.
- Combined pill PLUS condom: Normal and low-dose combined oral pills.
- Injection PLUS condom: Medroxyprogesterone injection (eg, Depo-Provera [Pfizer]).
- Implants PLUS condom: Etonogestrel-releasing implants (eg, Nexplanon [Merck Sharp & Dohme]).
- Patch PLUS condom: Norelgestromin/ethinyl estradiol transdermal system (eg, Xulane).
- Intravaginal device (eg, ethinyl estradiol-/etonogestrel-releasing intravaginal devices such as NuvaRing [Merck Sharp & Dohme]) PLUS condom.
- Levonorgestrel-releasing intrauterine system (eg, Mirena [Bayer]) PLUS condom.

5 CORRELATIVE STUDIES FOR RESEARCH

5.1 BIOSPECIMEN COLLECTION

5.1.1 Phase I and Phase II Cohorts

Table 11. Correlative studies

Phase I

Sample	Assay	Time points	Type of tube/sample ^a	Amount of blood
Optional Tumor (only in patients with SCLC)	gH2AX	(1) Pre-treatment on C1D1 (2) Pre-treatment C1D4 (24hr after olaparib) (3) At disease progression	NA	NA
	SLFN11 IHC SLFN11 gene expression		NA	NA
	Exome/RNAseq/ droplet digital PCR		NA	NA
Whole blood (only in patients with SCLC)	Germline DNA	(1) Pre-treatment	Purple top EDTA	5 ml
	Circulating tumor DNA mutation analyses	(1) Pre-treatment	Lavender top tubes	Three 10-ml
	Immune subsets (Peripheral blood mononuclear cells)	(1) Pre-treatment on C1D1 (2) Pre-treatment C1D3 (pre-olaparib) (3) C1D4 (24hr after olaparib) (4) Pre-treatment C2D1	CPT citrate blue/black tubes	Two 8-ml tubes
	Circulating tumor cells enumeration RAD51 foci	(1) Pre-treatment on C1D1 (2) Pre-treatment C2D1 (3) At disease progression	Lavender top tubes	Two 10-ml

Sample	Assay	Time points	Type of tube/sample ^a	Amount of blood
	Nanostring immune panel (770 genes)	(1) Pre-treatment on C1D1 (2) Pre-treatment C2D1 (3) At disease progression	PAXgene RNA	One 2.5 ml
	Nanostring DNA damage response panel (180 genes) ^{3,4}	(1) Pre-treatment on C1D1 (2) Pre-treatment C2D1 (3) At disease progression	PAXgene RNA	One 2.5 ml
Whole Blood (in all phase I patients)	gH2AX	(1) Pre-treatment on C1D1 (2) Pre-treatment C1D3 (pre-olaparib) (3) C1D4 (24hr after olaparib)	green top	One 6-ml tube
Hair (optional)	gH2AX	(1) Pre-treatment on C1D1 (2) Pre-treatment on C1D3 (pre-olaparib) (3) C1D4 (24hr after olaparib) (4) End of each cycle (any time after the last dose of olaparib but prior to the next dose of EP0057)	12 follicles	12 follicles
Plasma	PK	Refer to Table 12	Refer to Table 12	
a. Please note that tubes and media may be substituted based on availability with the permission of the PI or laboratory investigator.				

Phase II SCLC only

Sample	Assay	Time points	Type of tube ^a	Amount of blood	Lab/ Instruction
Tumor (Optional)	gH2AX	(1) Pre-treatment C1D1 (2) Pre-treatment C1D4 (24hr after olaparib) (3) At disease progression	NA	NA	Please call DTB Clinical Translational Unit when the samples are ready for pick- up at [contact] [name]
	SLFN11 IHC		NA	NA	
	SLFN11 gene expression		NA	NA	
Whole Blood	Exome/RNAseq/droplet digital PCR				Keep all tubes at room temperature
	Germline DNA	Pre-treatment	Lavender top EDTA	5 ml	
	Immune subsets (Peripheral blood mononuclear cells)	(1) Pre-treatment on C1D1 (2) Pre-treatment on C1D15 (3) Pre-treatment on C2D1 (4) At disease progression	CPT citrate blue/black tubes	Two 8-ml tubes	
	Circulating tumor cells enumeration	(1) Pre-treatment C1D1 (2) Pre-treatment C2D1 (3) At disease progression	CellSave tubes	One 10 ml	
	Nanostring immune panel (770 genes)	(1) Pre-treatment C1D1 (2) Pre-treatment C2D1 (3) At disease progression	PAXgene RNA	One 2.5 ml	
a. Please note that tubes and media may be substituted based on availability with the permission of the PI or laboratory investigator.					

5.1.1.1 γ -H2AX

Phosphorylated H2AX (γ -H2AX) plays an important role in the recruitment and/or retention of DNA repair and checkpoint proteins such as BRCA1, MRE11/RAD50/NBS1 complex, MDC1 and 53BP1. DNA damage has been shown to increase H2AX phosphorylation in cancer cells following exposure to camptothecins. If olaparib is able to increase the degree of DNA damage due to EP0057, it may be detectable by measurement of H2AX phosphorylation. We plan to study patient PBMCs, hair follicles, and tumor biopsies if obtained. Tumor tissue (optional) and hair follicles will be obtained if patients are suitable candidates and willing to allow such sampling. The ideal biomarker would confirm that there was increased DNA damage following addition of olaparib relative EP0057 alone. This analysis will be exploratory only and data will be used in planning biomarker endpoints in subsequent trials with the combination of EP0057 and olaparib.

Hair follicles will be collected at multiple time points per **Table 11**. At least 24 hours prior to the start of the study, the research nurse will contact [name] in [name] lab (DTB-LMP/CCR/NCI, [name]) to inform him when samples will be taken ([contact] (L); [contact] (Cell); [contact]). [name] will provide tubes for collecting the plucked hairs. The tubes contain ice cold PBS labeled with the date/time of sampling, the protocol, and the unique identifier. [name] will also provide forceps for plucking. [name] should be notified of when the samples should be picked up.

Single hairs are plucked from the scalp with forceps. Plucked hairs from eyebrows will be collected only if scalp hairs cannot be provided. The aim is to acquire 12 hairs that contain a full intact follicle and sheath. All the hairs from a patient are placed in microfuge tubes containing cold PBS and stored on ice. Upon delivery in [name] lab, hairs will be fixed with paraformaldehyde and analyzed under a dissection microscope to select those containing a full intact follicle and sheath. Plucked hairs will be fluorescently stained for γ -H2AX and images will be recorded by using a confocal microscope.

Blood will be collected per **Table 11**. When the patient is scheduled, the DTB Clinical Translational Unit will be contacted [by email to [contact]]. Blood from heparinized syringe will be mixed with a 1:1 ratio of room temperature PBS and layered over a 1:1 blood-PBS/Ficoll ratio in a conical centrifuge tube. The conical centrifuge tube should be centrifuged 25 minutes at room temperature at approximately 1000 rpm. The cell layer resting above the Ficoll and containing the peripheral blood mononuclear cells (PBMCs) will be aspirated and transferred to a 15 ml conical tube for washing in 15 ml PBS. PBMCs will be fixed with paraformaldehyde, spun onto a microscope slide and stain for γ H2AX detection. Images from γ -H2AX-stained PBMCs will be recorded by using a confocal microscope.

5.1.1.2 SLFN11

Expression of the gene SLFN11 has been found to correlate with the activity of topoisomerase inhibitors in studies using the National Cancer Institute cell line panel (NCI60) and the Cancer Cell Line Encyclopedia (CCLE) ([54](#), [55](#)). SLFN11 expression predicted sensitivity to DNA damaging chemotherapy including Top1 and Top2 inhibitors, alkylating agents, platinum derivatives, DNA synthesis and PARP inhibitors ([54-56](#)). In experiments using cells with endogenously high and low SLFN11 expression and siRNA- and Crispr-mediated silencing,

SLFN11 was found to be causative in determining cell cycle arrest and cell death in response to DNA damaging agents in cancer cells (56). Data from the CCLE, the NCI60 and The Cancer Genome Atlas (TCGA) indicate a broad range of SLFN11 expression in lung cancers, raising the possibility that high SLFN11 expression might enrich for tumors that are more likely to respond to DNA damaging chemotherapy; conversely low SLFN11 expression may predict tumors that are likely resistant. Pre-treatment SLFN11 expression in tumor samples will be assessed (IHC and RNA) to assess in an exploratory manner, the potentially role of SLFN11 as a predictor of response to EP0057 plus olaparib.

5.1.1.3 Tumor biopsies and genomic DNA

Biopsies will be done only in phase II part of the study and in SCLC patients in the phase I part of the study.

Paired tumor biopsies will be obtained by minimally invasive methods such as CT guided percutaneous biopsies before and after treatment [C1D4 (24hr after olaparib)] and at disease progression per **Table 11**. The site of biopsy will be determined in discussion with interventional radiologist. If it can be safely obtained, 4 cores of tumor tissue will be collected. Two cores will be sent to pathology- one for confirmation of diagnosis and another will be used for making an FFPE block. The other 2 cores will be flash frozen at the time of biopsy. When the patient is scheduled, the DTB Clinical Translational Unit lab will be contacted [by email to [name] [contact]]. Interventional Radiology will call the lab at [contact] when the patient arrives in IR and a lab member will be present at Interventional Radiology for the procedure. The cores will be flash frozen, 2D barcoded, and stored in liquid nitrogen.

Formalin fixed paraffin embedded tumor tissue (FFPE) from the new biopsies and or from archived FFPE tissue from prior biopsies/surgical procedures will be sent to the DTB Clinical Translational Unit as described above. Genomic DNA and RNA will be extracted from the tumor and archived for genomic analysis. Tumor tissue when obtained before start of treatment will be used for the following assessments: γ -H2AX, SLFN11, and POLQ expression; post-treatment biopsy samples will be assessed for γ -H2AX expression.

5.1.1.4 Immune Subsets

Little is known of the immunomodulatory effects of DNA damage-inducing cytotoxic therapy. Peripheral blood mononuclear cells (PBMC) will be obtained per **Table 11** and will be assessed by the DTB Clinical Translational Unit using multiparameter flow cytometry for immune subsets including but not necessarily limited to Tregs, myeloid-derived suppressor cells, effector and exhausted CD4+ and CD8+ T-cells, and CD14+ monocytes. Assessment will include functional markers, i.e. PD-1, Tim-3, CTLA-4, CD40, HLA-DR, and/or PD-L1. Members of the lab will procure the peripheral blood samples, enter the samples in a secure patient database, process the samples for viable cell storage, label each sample with a unique 2D barcode, and viably store the samples. They will prepare the samples for staining, stain and run the samples by multiparametric flow cytometry (MACSQuant, Miltenyi Biotec, Bergisch Gladbach, DE), the data will be analyzed by FlowJo v.X.0.6. Peripheral blood will be drawn into two 8-ml CPT citrate blue/black tubes for each time point. These assessments will be performed by the DTB Clinical Translational Unit.

Accumulating evidence has revealed the interplay between the host immune system and anticancer therapies.(57, 58) Several classical chemotherapeutics and molecular-targeted

therapies have been reported to stimulate tumor-specific immune responses either by inducing immunogenic cell death (ICD) or by engaging immune effector mechanisms. We propose to study the impact of combination therapy of EP0057 with olaparib on immune subsets and test for clinical relevance. These analyses offer the opportunity to obtain new insights into the immunomodulatory action of these combination therapies.

5.1.1.5 Circulating Tumor Cells and Circulating Tumor DNA

Circulating tumor cells (CTCs), which can be prevalent in SCLC, present a readily accessible 'liquid biopsy'. Peripheral blood will be collected per **Table 11** to correlate circulating tumor cell (CTC) levels at baseline or levels pre- and post-therapy with clinical response and survival. CTCs will be assessed using ferrofluidic enrichment and multiparameter flow cytometric detection. CTCs will be identified as viable, nucleated cells, that positively express one or more epithelial or tumor markers and are negative for expression of hematopoietic markers. CTCs will be enumerated and if sufficient, additional characterization performed included RAD51 foci, gene expression by droplet digital PCR, NanoString, whole transcriptome by Illumina or another platform as appropriate to the sample. Peripheral blood will be drawn into two 10-ml lavender top tubes and one 2.5 ml PAXgene RNA tube for each time point. These assessments will be performed by the DTB Clinical Translational Unit.

Circulating tumor DNA will be isolated from plasma separated from peripheral blood. Mutations identified by analysis of patient tumor samples may be included as personalized tumor markers in the circulating nucleic acid analysis. Mutations will be assessed by the appropriate technology. A multiplexed gene expression approach to profiling immune gene and DNA damage response signatures

Peripheral immune and DNA damage response transcriptional signatures will be evaluated by the DTB Clinical Translational Unit using the NanoString nCounter® platform (NanoString Technologies, Seattle, WA). We will use the nCounter 770 gene PanCancer Immune Profiling Panel and the newly released 170 gene DNA Damage & Repair panel, built in collaboration with the Developmental Therapeutics Branch. Peripheral blood will be collected in a PAXgene tube (PreAnalytix; 2.5 cc peripheral blood per tube) per the manufacturer's instructions. RNA will be isolated using the PAXgene Blood RNA Kit according to the manufacturer's instructions. The peripheral gene signatures will be evaluated at baseline and post-therapy to look for correlates of clinical response.

5.1.1.6 PK (Phase I only)

In Phase I only, blood samples for the determination of EP0057 and olaparib plasma levels will be obtained from participating patients via 6mL sodium heparin tube (BD, Franklin Lakes, NJ) per the table below. Samples will be obtained following the first dose on Cycle 1, day 1, and again on Cycle 6, day 1 in order to assess the extent of accumulation from repeated dosing at the time points specified below:

Table 12. Phase I PK Sample Collection Timeline

sample	cycle	day	time (approx.)	hr post-EP0057 start	post-olaparib
1	1	1	8:00a	0 hr (predose, may be drawn 24 hrs prior start of dosing)	-
2	1	1	8:30a	0.5 hr [+/- 5 minutes] (mid-infusion)	-
3	1	1	9:00a	1 hr [+/- 5 minutes] (end of infusion (EOI))	-
4	1	1	10:00a	2 hr [+/- 5 minutes] (1 hr post EOI)	-
5	1	1	11:00a	3 hr [+/- 5 minutes] (1 hr post EOI)	-
6	1	1	9:00p	13 hr [+/- 60 minutes] (12 hr post EOI)	-
7	1	2	9:00a	25 hr [+/- 60 minutes] (24 hr post EOI)	-
8	1	3	10:00a	50 hr [+/- 120 minutes] (49 hr post EOI)	2 hr
9	1	15	8:00a	360 hr [+/- 5 days] (359 hr post EOI)	-
10	6	1	8:00a	0 hr (predose, may be drawn 24 hrs prior start of dosing)	-
11	6	1	8:30a	0.5 hr [+/- 5 minutes] (mid-infusion)	-
12	6	1	9:00a	1 hr [+/- 5 minutes] (end of infusion (EOI))	-
13	6	1	10:00a	2 hr [+/- 5 minutes] (1 hr post EOI)	-
14	6	1	11:00a	3 hr [+/- 5 minutes] (1 hr post EOI)	-
15	6	1	9:00p	13 hr [+/- 60 minutes] (12 hr post EOI)	-
16	6	2	9:00a	25 hr [+/- 60 minutes] (24 hr post EOI)	-
17	6	3	10:00a	50 hr [+/- 120 minutes] (49 hr post EOI)	2 hr
18	6	15	8:00a	360 hr [+/- 5 days] (359 hr post EOI)	-

The PK samples will be placed immediately on wet ice and refrigerated. The date and exact time of each blood draw should be recorded on the sample tube and the PK sheet. Please e-mail the Blood Processing Core (BPC) at [contact] at least 24 hours before transporting samples (the Friday before is preferred). For sample pick up, please page [name]. For immediate help, call [contact] (main blood processing core number) or, if no answer, [contact] (main clinical pharmacology lab number).

Bioanalytical measurements of EP0057 and olaparib will be measured by individual ultra HPLC-MS/MS assays optimized for each drug by the Clinical Pharmacology Program (CPP). This data will be used to assess any drug-drug interactions are present between olaparib and EP0057, as well as to correlate adverse events and efficacy to each drug's exposure. Neither olaparib nor camptothecin are extensively metabolized into pharmacologically active metabolites, therefore there are no relevant pharmacogenomic considerations regarding drug metabolizing enzymes or transporters with this combination.

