1.1.2 Secondary Objectives

Phase I and Phase II Cohorts:

- 1.1.2.1 To evaluate the pharmacokinetic profile of EP0057 (both the total drug and released camptothecin) and olaparib in plasma.
- 1.1.2.2 To evaluate the pharmacodynamic (PD) activity of EP0057 in blood, surrogate tissue and tumor biopsy specimens.
- 1.1.2.3 To determine the duration of response (DOR), overall survival (OS), and progression-free survival (PFS) of the combination.
- 1.1.2.4 To further explore safety for combination.

Phase II Expansion Cohorts:

- 1.1.2.5 To determine safety and progression-free survival (PFS) in patients with mCRPC and urothelial carcinoma.
- 1.1.2.6 To determine duration of response and PSA responses in patients with mCRPC.

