1.2.8 EP0057 phase I clinical trial

Patients with advanced solid malignancies were enrolled to an open-label, single-arm, dose-escalation study, in which EP0057 was administered intravenously over 60 min among two dosing schedules, initially weekly at 6, 12, and 18 mg/m² and later bi-weekly at 12, 15, and 18 mg/m². The MTD was determined at 15 mg/m² bi-weekly, and an expansion phase 2a study was completed. Sixty-two patients (31 male; median age 63 years, range 39-79) received treatment. Bi-weekly dosing was generally well tolerated with myelosuppression being the dose-limiting toxicity. Among all phase 1/2a patients receiving the MTD ($n=44$), most common grade 3/4 adverse events were neutropenia (Grade 3 neutropenia = 9% and no grade 4) and fatigue (Grade 3 fatigue = 9%, no grade 4). Evidence of systemic plasma exposure to both the polymer-conjugated and unconjugated CPT was observed in all treated patients. Mean elimination unconjugated CPT Tmax values ranged from 17.7 to 24.5 h, and maximum plasma concentrations and areas under the curve were generally proportional to dose for both polymer-conjugated and unconjugated CPT. Best overall response was stable disease in 28 patients (64 %) treated at the MTD and 16 (73 %) of a subset of NSCLC patients. Median progression-free survival (PFS) for patients treated at the MTD was 3.7 months and for the subset of NSCLC patients was 4.4 months.

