⁷ Includes Alkaline Phosphatase, ALT/GPT, AST/GOT, Total Bilirubin, Direct Bilirubin

⁸ Only for IOCBP; may be obtained up to 3 days prior to Day 1 of each cycle.

⁹ Blood, plasma, hair and saliva samples will be collected at multiple time points during cycles 1,2 and each cycle thereafter for hair collection (for specific timepoints on correlative samples collection please refer to section 5.1.1 for Phase I and Phase II cohorts, section 5.1.2 for UC expansion cohort and section 5.1.3 for mCRPC expansion cohort). C1D15 timepoint for correlative studies will only be done for Phase II SCLC cohort. Only whole blood will be drawn for that cohort at that timepoint.

¹⁰ Optional biopsies will be obtained at baseline, during the first treatment cycle (approximately 24 hours after the first dose of olaparib) and at disease progression. In the mCRPC cohort, biopsy at baseline is mandatory.

¹¹ PO days 3-13 and days 17-26, as indicated in Section 3.2. There should be at least a 48-hour window between EP0057 and olaparib except dose level 5B which allows the interval to be abbreviated to 24 hours. Olaparib can be taken continuously if EP0057 is missed for any reason.

¹² Performed after every 2 cycles

¹³ Approximately 4 weeks after treatment discontinuation

¹⁴ Only done in cycle 1

¹⁵ Only done in phase 2

¹⁶ Phase 1 portion of the study in cycles 1 and 6 only.

¹⁷ Within 3 months of C1D1.

¹⁹ D15 PKs can be obtained +/- 5 days.

²⁰ Weekly during C1, at every visit for subsequent cycles, and whenever clinically indicated

²¹ Within 4 weeks

²² C2 and all subsequent cycles, Day 1

²³ All patients should get tested at screening. Patients taking warfarin will be monitored at least weekly for C1, then monthly if the INR is stable.

²⁴ Includes Albumin, Calcium, Magnesium and Phosphorus

²⁵ PSA is to be analyzed along with measurable lesions evaluated by CT scan of chest/abdomen/pelvis and technetium 99 bone scan every 3 cycles (every 12 weeks).

²⁶ Hair collection will only be done for Phase I cohorts.

²⁷ ECG required within 60 -180 minutes post-infusion for first two cycles of EP0057 for patients with any conduction abnormality on baseline ECG.

²⁸ Day 15 assessments not required for patients on olaparib only.

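### The phase I PK table labels the Day 15 sample 360 h when its own convention gives 336 h, has no pre-infusion rule, and cannot deliver the olaparib profile and interaction assessment promised

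*Combined protocol and SAP*

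**What the plan says.** Section 1.1.2.1 sets a secondary objective for the phase I and II cohorts: "To evaluate the pharmacokinetic profile of EP0057 (both the total drug and released camptothecin) and olaparib in plasma". Section 5.1.1.6 (phase I only) schedules nine samples in cycle 1 and nine in cycle 6, to be assayed for both drugs, and names accumulation over repeated dosing as the purpose. On use of the results it says "This data will be used to assess any drug-drug interactions are present between olaparib and EP0057", and it adds that toxicity and efficacy will be related to exposure to each drug.

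Table 12 starts its clock at Day 1, 8:00a, with "0 hr (predose, may be drawn 24 hrs prior start of dosing". The next-morning sample is "25 hr [+/- 60 minutes] (24 hr post EOI". The Day 15, 8:00a sample is "360 hr [+/- 5 days] (359 hr post EOI". Footnote 19 of the study calendar (section 3.4) repeats the window: "D15 PKs can be obtained +/- 5 days". The 11:00a sample is labelled "3 hr [+/- 5 minutes] (1 hr post EOI", the same interval after the end of infusion (EOI) as the 10:00a sample.

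EP0057 is infused on Days 1 and 15 (section 3.1). Olaparib is taken on Days 3-13 and 17-26 (section 3.2.2); the pill diary in Appendix C shows only a morning dose on Days 13 and 26.

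**The concern.** There are three problems.

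First, the Day 15 label does not match its own day and clock time. Because EP0057 is given again on Day 15, it matters whether the sample is the tail of the first dose or an early point of the second. Section 1.2.8 reports that "unconjugated CPT Tmax values ranged from 17.7 to 24.5 h". A draw that slipped to a day after the second infusion would therefore sit near the peak of released camptothecin from that dose. The window permits such a draw, and nothing says how it would be analysed. Section 14.1.6 itself worries about carry-over of released camptothecin between doses, which a pre-infusion Day 15 sample would help to check.

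Second, two samples an hour apart carry the same time after the end of infusion.

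Third, the stated olaparib profile, the interaction assessment and the exposure correlations need olaparib sampling that the schedule does not contain. At stake is whether the report makes PK statements that the data cannot carry.

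**Working it through.** **Elapsed time.** Take Day 1, 8:00a as 0 h, as Table 12 does. Hours from EP0057 start = (day - 1) x 24 + (clock time - 8:00).

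| Sample (cycle 1 / 6) | Day, clock | Computed | Table 12 |
|---|---|---|---|
| 1 / 10 | 1, 8:00a | 0 | 0 |
| 2 / 11 | 1, 8:30a | 0.5 | 0.5 |
| 3 / 12 | 1, 9:00a | 1 | 1 |
| 4 / 13 | 1, 10:00a | 2 | 2 |
| 5 / 14 | 1, 11:00a | 3 | 3 |
| 6 / 15 | 1, 9:00p | 13 | 13 |
| 7 / 16 | 2, 9:00a | 24 + 1 = 25 | 25 |
| 8 / 17 | 3, 10:00a | 48 + 2 = 50 | 50 |
| 9 / 18 | 15, 8:00a | 14 x 24 = 336 | **360** |

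Eight of nine rows reproduce. The ninth is off by 360 - 336 = 24 h, or 24/336 = 7%. The printed figure equals 15 x 24, which counts the day number as elapsed days and contradicts the Day 2 and Day 3 rows.

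**Window.** 336 ± 120 h is 216 to 456 h, which is Day 10 to Day 20. If the window were centred on the printed 360 h, it would be 240 to 480 h, Day 11 to Day 21. Either way it includes times before and after the scheduled Day 15 infusion, and days on and off olaparib.

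**Time after end of infusion.** Hours post EOI = hours from start - infusion duration. The protocol gives three durations: 1 h in Table 12 (EOI at 9:00a), 60-75 minutes in section 3.2.1, and about 2 h in section 3.2.1.1.

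| Infusion | 2 h sample (4, 13) | 3 h sample (5, 14) |
|---|---|---|
| 1 h | 1 h | 2 h |
| 75 min | 0.75 h | 1.75 h |
| 2 h | 0 h | 1 h |

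No duration makes both samples 1 h post EOI, so the table is inconsistent. Which label is wrong depends on the duration. The same holds for the Day 15 post-EOI value: 335 h with a 1 h infusion, 334 h with 2 h.

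**Olaparib sampling.** A planned time after olaparib appears for samples 8 and 17 only: 2 of 18, or 1 of 9 in each sampled cycle, both at 2 h on Day 3. On schedule, Days 1 and 2 precede that cycle's olaparib, and Day 15, 8:00a is about 48 h after the Day 13 morning dose. One timed concentration gives no AUC, Cmax, Tmax, half-life or clearance by non-compartmental methods. The documents describe no population model and no external olaparib reference that could fill the gap.

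**Interaction, by direction.**
- *EP0057 on olaparib:* no period on olaparib alone is sampled, so there is no reference.
- *Olaparib on EP0057:* cycle 1 samples to 25 h are olaparib-free, because olaparib starts on Day 3. The matching cycle 6 samples follow olaparib-free Days 27-28 of the previous cycle and come after repeated EP0057 dosing. Any difference mixes accumulation with a possible residual olaparib effect.

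**The case against.** The strongest reply is that the 360 h figure is a clerical slip with little consequence. The row also gives Day 15 and 8:00a, the same clock slot as the predose samples, so a site following those columns draws at the right time. Section 5.1.1.6 requires the date and exact time of every draw to be recorded, and no section prescribes analysis by nominal time. A label error common to both cycles would also largely cancel in a cycle 6 to cycle 1 ratio. All of this stands. A reader might infer that the plan schedules a draw at the second-dose camptothecin peak; it does not. Distortion of the terminal phase is a risk only under an analysis the documents do not describe.

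It can also be said that section 3.4 allows treatment delays of up to 7 days, so a late draw beside a delayed infusion may still be a valid pre-dose sample. That is right. It argues for a rule tied to the actual infusion rather than the calendar day; no such rule exists.

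A reader might further infer that neither drug has a single-agent reference. That is too broad: the early cycle 1 EP0057 samples are olaparib-free, and only olaparib lacks a reference. Nor can the 3 h samples simply be relabelled 2 h post EOI, since that presumes one of the conflicting infusion durations.

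Finally, PK is a secondary objective, the dose was chosen on DLTs, phase I is complete, and section 10 ties no decision to PK. This limits the severity but does not make the olaparib claims deliverable.

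**Conclusion.** The point holds, as a minor one. The Day 15 label is wrong by 24 h in two samples under the table's own convention. The window of about Days 10-20 allows draws on either side of the second infusion without a rule to tell them apart. The post-EOI labels of the 2 h and 3 h samples cannot both be right, and sections 3.2.1, 3.2.1.1 and Table 12 must be reconciled before either is changed.

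The part with more substance is the olaparib claim. With one 2 h concentration in each sampled cycle and no olaparib-alone sampling, the plan cannot yield an olaparib profile or exposure measure, or an estimate of EP0057's effect on olaparib. A cycle 1 versus cycle 6 comparison of EP0057 is possible but confounded with repeat dosing.

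These conclusions assume dosing and sampling on the scheduled days, and that no modelling or external reference exists outside the documents. The dose decision and the efficacy analyses are unaffected.

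**What to change.** - In Table 12, change samples 9 and 18 to 336 h from EP0057 start.
- Reconcile the infusion durations in Table 12 and sections 3.2.1 and 3.2.1.1. For analysis, compute every post-EOI time from the actual recorded end of infusion.
- State that PK will be analysed by actual times. Use a Day 15 sample in the first-dose profile and the accumulation comparison only if it was drawn before the second infusion.
- Restate sections 1.1.2.1 and 5.1.1.6 as an EP0057 profile plus a descriptive 2 h olaparib concentration. Drop the olaparib profile, any olaparib exposure estimate (and so correlations that rest on one), and any estimate of EP0057's effect on olaparib.
- Label any cycle 1 versus cycle 6 comparison of EP0057 as exploratory and confounded with repeat dosing.

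The cost is wording and analysis rules only, since the phase I part is complete and no new samples are needed. The downside is a narrower stated PK objective and possibly a few Day 15 samples excluded from the first-dose analysis.
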